1.5. Primary Objective

The primary objective of this study is to assess the safety and tolerability of treatment with NIVOLUMAB in combination with ipilimumab in subjects with resected Stages IIIB/IIIC/ IV melanoma.

1.6. Secondary Objectives

The secondary objectives of this study are to:

- evaluate the immune response to treatment with the study drugs at Week 12.
- assess the preliminary efficacy of the study drugs as defined by an assessment of time to relapse

2. OVERVIEW OF STUDY DESIGN

2.1. General Design and Study Schema

This is a pilot, phase II, open-label, single center, multi-dose, study of NIVOLUMAB in combination with ipilimumab. NIVOLUMAB is an FDA-approved fully human monoclonal antibody (HuMAb) against programmed death-1 (PD-1). (See STUDY DRUGS, DOSES, AND ADMINISTRATION). Ipilimumab is a FDA-approved fully human monoclonal antibody against cytotoxic T lymphocyte antigen-4 (CTLA-4)

The study will consist of 4 periods: Screening (up to 4 weeks), Treatment (up to 1 12-week cycle), Treatment/Follow-up (up to 1 year), and Survival Follow-up. Each treatment cycle is comprised of 4 doses of NIVOLUMAB and 4 doses of ipilimumab given every three weeks for a total of 12 weeks (cycle 1) with a tumor assessment at the end of cycle 1 at week 12.

At the end of the Treatment Period (Week 12) subjects without evidence of relapse radiologically and clinically will be able to continue to receive NIVOLUMAB with flat dosing at 480mg every 4 weeks for 48 additional weeks. Subjects who relapse at the disease evaluations at Weeks 12, 24 or later will not receive further treatment with NIVOLUMAB.

Patients who experience a DLT to NIVOLUMAB and ipilimumab during or after cycle 1 will not receive further treatment with NIVOLUMAB and ipilimumab.

Subjects who prematurely discontinue 1 or both study drugs will complete the remaining study visits and associated evaluations (without dosing of 1 or both study drugs, as applicable) indefinitely until withdrawal of consent for follow-up or death.

Dosing in cycle 1 will consist of: 3 mg/kg of NIVOLUMAB + ipilimumab at 1 mg/kg

Since the drugs will be given concurrently, it will not be possible to attribute dose-limiting toxicities to one or the other drug during the first 12 weeks of therapy.

Subjects who withdraw from the study during Cycle 1 for reasons other than a DLT will be replaced.

No dose escalations or de-escalations are permitted within each subject's treatment. NIVOLUMAB or ipilimumab dose adjustments are allowed only if there has been $\pm 10\%$ weight change since the previous treatment (Induction Treatment Period only). No dose escalations or de-escalations are allowed during cycles 2-5 due to the use of flat dosing of NIVOLUMAB at 480 mg every 4 weeks.

2.2. Primary Endpoint

The primary efficacy analysis is time to relapse. Time to relapse will be summarized using descriptive statistics. Scanning and exams to detect recurrence will be conducted every 3 months until 2 years from finishing treatment, then every 6-12 months (minimum of every 12 months) for 2 years, then yearly thereafter.

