Serum samples will be collected and cryopreserved to study molecules that may be implicated in regulating anti-melanoma immune responses and/or NIVOLUMAB or ipilimumab activity such as soluble MICA, compounds detected by mass spectroscopy including those associated with wound healing, complement and the acute phase response, chemokines or cytokines, or antibodies to melanoma antigens.

Efficacy

Using imaging results (computed tomography/magnetic resonance imaging [chest, abdomen, pelvis, and brain] and photography of lesions) as well as clinical examination, presence of relapse will be evaluated and treatment decisions will be made by the Investigator (who is also the Sponsor). Scans and measurements may be reviewed by independent radiologists at a later date or any time during the study.

The primary efficacy endpoint is relapse free survival as determined by the results of Investigator evaluations.

STATISTICAL METHODS

A sample size of up to 20 subjects with 5 additional patients to accommodate drop-outs is based on the study design for safety evaluation requirements.

The incidence, relationship to therapy, and severity of adverse events will be summarized using descriptive statistics. Changes in clinical laboratory tests, ECOG, vital signs, ECGs, chest radiography, and immune safety results will be summarized using descriptive statistics. Immunogenicity results will be provided as a listing.

Immune response will be summarized using descriptive statistics..

Efficacy evaluations (RFS) will be summarized using descriptive statistics.

ABBREVIATION

Abbreviation	Term
β-HCG	beta human chorionic gonadotropin
AIDS	acquired immunodeficiency syndrome
ALT	alanine aminotransferase
APC	antigen-presenting cells
AST	aspartate aminotransferase
BMS	Bristol-Myers Squibb
BOR	Best Overall Response
BORR	Best Overall Response Rate
CI	confidence interval
CR	Complete Response
CRF	case report form
CTCAE	Common Terminology Criteria for Adverse Events
CTEP	Cancer Therapy Evaluation Program
CTLA-4	cytotoxic T lymphocyte-associated antigen 4
DC	dendritic cells
DLT	dose-limiting toxicity
DNA	deoxyribosenuclelic acid
ECG	electrocardiogram
ECOG	Eastern Cooperative Oncology Group
ESI	event of special interest
FDA	Food and Drug Administration
GCP	Good Clinical Practice
GI	Gastrointestinal
HBV SAg	hepatitis B virus surface antigen
HCV RNA	hepatitis C virus ribonucleic acid
HIV	human immunodeficiency virus
HPF	high power field
HuMAb	human monoclonal antibody

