4.2.6. Stopping Rules for Clinical Deterioration

Accumulating clinical evidence indicates that the emergence of objective responses to agents that activate anti-tumor immune responses may follow delayed kinetics of weeks or months, and can be preceded by initial apparent progression with appearance of new lesions or some enlarging lesions while certain index lesions are regressing (“mixed response”). It is thus reasonable to allow subjects experiencing apparent relapse in this trial to continue to receive treatment until relapse is confirmed at the next imaging assessment. These considerations should be balanced by clinical judgment as to whether the subject is clinically deteriorating and unlikely to receive any benefit from continued treatment.

Such deterioration will be assessed to have occurred after a clinical event that, in the Investigator’s opinion, is attributable to disease relapse, is unlikely to reverse with continued study treatment and therefore indicates that the subject is not benefiting from study treatment. Examples of events that may, in the Investigator’s opinion, indicate a lack of clinical benefit include, but are not limited to, the following:

- Performance status decrease of at least 2 points from baseline.
- Skeletal related events defined by the following:
 - pathologic bone fracture in the region of cancer involvement,
 - cancer related surgery to bone, and
 - spinal cord or nerve root compression.
- Development of new central nervous system metastases.

Or any setting where the initiation of new anti-neoplastic therapy has been deemed beneficial to the subject even in the absence of any such documented clinical events.

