6.3. Statistical Analysis

The data collected in this study will be analyzed by the Biostatistics group at the Perlmutter Cancer Center at NYU.

All data will be listed individually by subject. For quantitative parameters, descriptive statistics will include the mean, standard deviation, minimum, median, and maximum. For qualitative parameters, descriptive statistics will include frequency and percentage.

Unless otherwise indicated, the statistical significance will be declared if the two-sided p-value is ≤ 0.05 .

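### The main efficacy endpoint has two non-equivalent names and only unspecified descriptive statistics, with no event definition, censoring rule or time-to-event estimator

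*Combined protocol and SAP*

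**What the plan says.** **Name.** Section 1.6 sets as a secondary objective to "assess the preliminary efficacy of the study drugs as defined by an assessment of time to relapse", and the Synopsis objectives and section 2.2 also speak of time to relapse. The Synopsis efficacy paragraph says: "The primary efficacy endpoint is relapse free survival as determined by the results of Investigator evaluations". Sections 3.4.6.1, 4.2.4.1 and 5.4 also use relapse-free survival. None of them defines it.

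**Method.** Section 2.2: "The primary efficacy analysis is time to relapse. Time to relapse will be summarized using descriptive statistics". Synopsis, Statistical Methods: "Efficacy evaluations (RFS) will be summarized using descriptive statistics". Section 6.3 explains the term: "For quantitative parameters, descriptive statistics will include the mean, standard deviation, minimum, median, and maximum"; "For qualitative parameters, descriptive statistics will include frequency and percentage"; and "All data will be listed individually by subject". Section 6.3 has subsections for demographics, concomitant medication, safety and immunology, but none for efficacy. Section 6.12.2 names only the efficacy populations (Safety and Evaluable). Section 6.4 allows conservative imputation, with an adverse-event date as its one example.

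**What is settled.** The investigator judges relapse (Synopsis, section 5.4). Treatment may continue after an apparent relapse "until relapse is confirmed at the next imaging assessment" (section 4.2.6), and section 5.4 expects confirmation in some cases. Table 1 footnote 10 has the progression date recorded. Overall survival is the secondary efficacy endpoint (section 2.3), with no method given.

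**Imaging.** Section 2.2 has assessments every 3 months until 2 years after the end of treatment, then every 6 to 12 months for 2 years, then yearly. Table 1 footnote 9 has imaging every 6 to 12 months over a first two-year span whose start is not stated, then every 12 months.

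**The concern.** Time to relapse is a censored quantity. A patient who is relapse-free at analysis, withdraws, or is lost (section 3.4.6.2 foresees the last two) has no relapse time. Anyone who received even a partial dose is in the Safety Population (section 6.2.1), on which efficacy is analysed, so such patients cannot simply be set aside. A mean, SD or median is then undefined until someone decides how to enter them, and the plan leaves that decision to be made after the data are seen.

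The two names add a second open choice. Relapse-free survival ordinarily counts death without relapse as an event; time to relapse need not. Also unstated are the time origin, and whether the first or the confirming scan supplies the date when relapse is confirmed later.

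At stake is whether the trial's leading efficacy result can be reproduced and compared with other adjuvant cohorts. The safety conclusion is not affected.

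**Working it through.** The documents give no relapse rate, accrual period or loss rate, so there is no plan figure to reproduce. Everything below rests on assumed values with exponential relapse, to show direction and size.

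**1. Plain mean and median.** Assume 24-month RFS S, so hazard h = −ln(S)/24 per month. Suppose everyone is followed for C months and relapse-free patients are entered at C. Then:
- true median = ln 2 / h
- plain median = the smaller of C and ln 2 / h
- plain mean = (1 − e^(−hC)) / h
- mean in relapsers only = 1/h − C·e^(−hC) / (1 − e^(−hC))

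For S = 0.65, h = 0.4308/24 = 0.01795 and the true median is 0.6931/0.01795 = 38.6 months.

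| Follow-up C (months) | Plain median | Plain mean | Mean, relapsers only |
|---|---|---|---|
| 12 | 12 | 10.8 | 5.8 |
| 24 | 24 | 19.5 | 11.1 |
| 36 | 36 | 26.5 | 16.1 |

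The same disease course gives a median that simply equals follow-up. Over the assumed range of S:
- S = 0.80: the plain median is again 12, 24, 36, against a true 74.6.
- S = 0.50: true median 24.0. The plain median is right at 24 and 36 months, but the mean still moves from 17.3 to 22.4.
- S = 0.30: true median 13.8. The plain median is right at 24 and 36 months, and the mean moves from 14.0 to 16.7.

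So the plain median fails when fewer than half have relapsed within follow-up. The mean depends on follow-up throughout.

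**2. Crude 24-month percentages.** Assume S = 0.65, everyone due at least 24 months of follow-up, and a proportion D lost by month 24 at a constant rate d = −ln(1 − D)/24. Then:
- known relapse-free, over all patients: A = 0.65 × (1 − D)
- relapse recorded: R = [h/(h + d)] × (1 − A)
- no relapse recorded, over all patients: 1 − R
- known relapse-free, over patients of known status: A/(A + R)

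| Assumed D | No relapse recorded | Known relapse-free / all | Known status only | True value (Kaplan-Meier target) |
|---|---|---|---|---|
| 0% | 65.0 | 65.0 | 65.0 | 65.0 |
| 5% | 65.8 | 61.8 | 64.4 | 65.0 |
| 10% | 66.7 | 58.5 | 63.7 | 65.0 |

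Example, D = 10%: A = 0.65 × 0.90 = 0.585; d = 0.1054/24 = 0.00439; R = (0.01795/0.02234) × 0.415 = 0.333; 0.585/0.918 = 0.637.

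With complete follow-up the percentages agree and Kaplan-Meier adds nothing at that landmark. With drop-out they separate, and counting unknown patients as failures moves the figure most.

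**3. Undefined event date and role of death.** Dating every relapse at a confirming scan 12 weeks (2.76 months) later changes 12-month RFS by e^(−9.24h) − e^(−12h) = 0.847 − 0.806 = 4.1 points at S = 0.65. This is a ceiling, since confirmation applies to selected cases only. If the net probability of death without relapse by month 24 is an assumed 5%, counting those deaths lowers 24-month RFS by 0.65 × 0.05 = 3.3 points. Both are below the sampling SD of a Kaplan-Meier estimate at n = 25 (about 10 points in simulation), but they are systematic.

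**The case against.** The strongest reply is that this is a small safety pilot in which a descriptive efficacy summary is proper. Kaplan-Meier is itself descriptive, section 6.3 gives an open list that includes the median, and individual listings plus recorded progression dates let anyone re-analyse. All of that stands. It limits the severity, and no hypothesis test is being asked for. It does not supply the event definition, the time origin or a censoring rule.

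Four stronger readings are tempting, and the documents do not support them.

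- *The plan commits to a biased mean or median.* It does not. No section says how relapse-free patients would be entered, so the first table shows what one permitted reading would give, not a predicted error.
- *The five extra places imply 20% loss to follow-up.* They are an enrolment allowance. Section 4.9 ties replacement to untreated subjects and to withdrawal before the end of cycle 1 for reasons other than a DLT, and section 6.1 also mentions screening failures. No longer-term loss rate follows from them.
- *Many patients will lack 24 months of follow-up at analysis.* No calendar cut-off is set. Section 2.5 expects up to 3 years' participation per subject, section 5 extends follow-up for relapse and survival indefinitely, and sections 3.4.6.1 and 4.2.4.1 keep patients who stop drug on the radiology schedule.
- *The imaging schedules flatly contradict each other.* Footnote 9 closely resembles the later phase in section 2.2 and may describe only that phase; footnotes 12 and 13 give 12-weekly assessments. Table 1 is also broken in the supplied text. This is an ambiguity to resolve, not a proven conflict.

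**Conclusion.** The point holds, with minor-to-moderate severity. The main efficacy endpoint carries two names that differ on death without relapse. It is assigned only descriptive statistics, with no time origin, event-date rule, censoring rule or time-to-event estimator; overall survival has no method either. Applied literally to censored times, the listed summaries are undefined or follow the length of follow-up: 12, 24 or 36 months against a true median of 38.6 at an assumed 24-month RFS of 65%.

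The size depends on assumptions that the documents cannot settle. If half the patients relapse within follow-up, the plain median is correct. If nobody is lost before month 24, crude percentages match Kaplan-Meier. At an assumed 5% to 10% loss, two of the three crude versions lie within about 2 points of the true value, while counting unknowns as failures is 3 to 7 points low. The consequence is confined to the efficacy report: safety is the primary objective (section 1.5), the sample size rests on safety and immune assays (section 6.1), and the stopping rule in section 4.2.5 uses DLTs.

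**What to change.** Add an efficacy subsection to section 6.3 and align the Synopsis and sections 1.6 and 2.2 with it:

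- Use one name, RFS, with relapse or death from any cause as the event.
- State the time origin (for example, first dose), and which date counts when relapse is confirmed at a later scan.
- Censor patients without an event at their last disease assessment.
- Replace the mean and SD summary with Kaplan-Meier estimates and 95% confidence intervals in the Safety and Evaluable populations, giving the median only if it is reached.
- Estimate overall survival by Kaplan-Meier, censored at the date last known alive.

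Separately, the sponsor should reconcile section 2.2 with Table 1 footnote 9 and state when the footnote's two-year span begins, because the scan interval affects the recorded relapse date.

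The cost is a few lines of statistical text and a clarifying amendment on imaging. The analysis changes need no new data, since progression dates and survival status are already collected.

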2.3. Secondary Endpoint

Overall survival will be the secondary efficacy endpoint; patients will be followed for survival indefinitely as indicated in the study schema.

2.4. Benefit/risk ethical assessment

2.4.1 Benefit

The potential benefits to subjects with study participation are improved overall survival. The information obtained from this research may help others with this disease in the future.

2.4.2 Potential Risks of Study drugs

NIVOLUMAB and Ipilimumab

In the Phase 1 MDX1106-01 (single dose [with possible retreatment] cancer) study a single instance of an inflammatory colitis serious irAE has been reported. This event occurred after the subject received 5 doses of 1 mg/kg NIVOLUMAB administered over 8 months and approximately 8 weeks after the last dose was administered. Twenty-one subjects have safely received at least 1 dose of 10 mg/kg, 6 received 2 or more 10 mg/kg doses, including 1 subject who has received 9 (10 mg/kg) doses over 18 months. Low grade irAEs have included arthropathies and declines in thyroid-stimulating hormone. Administration of NIVOLUMAB in the ongoing MDX1106-02 (single dose hepatitis) and MDX1106-03 (multiple dose cancer) studies has been well tolerated to date. In the current BMS CA209007 adjuvant study, no DLTs

have been observed during the 29 day DLT period, but two episodes of grade 3 colitis have been observed after week 12, causing treatment with vaccine plus NIVOLUMAB to be discontinued. Both patients recovered fully with prolonged steroid tapers and are currently free of disease more than a year after the episode(s) of colitis.

Other possible toxicities with NIVOLUMAB, and ipilimumab may be anticipated based on general experience with other mAbs, preclinical data, and clinical studies with similar investigational agents. Possible toxicities could affect the immune system, hematologic, cardiovascular, hepatic, musculoskeletal, and other systems, and may include:

- **Infusion reactions:** Fever, chills, shakes, itching, rash, hyper- or hypotension, difficulty breathing. It is likely that most infusion-related adverse events will occur within the first 24 hours after beginning the infusion, and may be treated by slowing or interruption of the infusion, or with supportive treatment as indicated in Section 5.2.2.
- **Widespread immune activation/cytokine storm:** Cytokine storm adverse events may initially look like allergic reaction/hypersensitivity, but are distinguished by more sustained and profound hemodynamic disturbances related to the widespread release of cytokines such as IL-1 and tumor necrosis factor (TNF). Symptoms may include fever, myalgia, change in mental status, hypotension, pulmonary infiltrates, metabolic acidosis and acute renal failure. Cytokine storm has been observed with an agonistic anti-CD28 antibody (TGN1412), but is not expected with NIVOLUMAB and/or ipilimumab, and has not been observed in human subjects with cancer or hepatitis C treated to date.
- **Immune-related adverse events:** It is possible that syndromes may develop that are most consistent with an underlying enhanced immune response as the driving factor. Such events may consist of persistent rash, diarrhea and colitis, autoimmune hepatitis, arthritis, glomerulonephritis, or cardiomyopathy. Experience with ipilimumab indicates that irAEs are typically low grade and self limited, more often occur after multiple doses, and most frequently involve the GI tract (diarrhea/colitis), skin (rashes), liver (hepatitis), and endocrine systems (a variety of endocrinopathies). See. section 8.5.
- **Gastrointestinal system:** Colitis is characterized by new onset of diarrhea, which may be accompanied by abdominal pain and/or GI bleeding. Events of Grade 3 or Grade 4 diarrhea as well as Grade 2 diarrhea with blood in stool should be evaluated for colitis. Subjects should be instructed to report all events of diarrhea immediately to the Investigator. **Any \geq Grade 2 diarrhea/colitis must be reported to the BMS, within 24 hours using the rapid notification procedures described in Section 8.6.**
- **Inflammatory hepatotoxicities:** Hepatotoxicity has been observed in the ipilimumab program, and in the concurrent NIVOLUMAB/ipilimumab study⁵⁸. Hepatocytes have been shown to express PD-L1 in the setting of IFN- γ and may occur in the presence of inflammation due to chronic viral hepatitis or immune-related heightened reactivity. PD-1 blockade may result in enhanced hepatic inflammation.

- **Immune suppression:** Subjects should be monitored for signs of new infection or return of a previous infection, with rash, fever, chills, other localizing symptoms, or sepsis that could require antibiotics either as prevention or treatment.
- **Musculoskeletal system:** Muscle or joint aches, swelling, or weakness.
- **Blood:** A decrease in blood components (platelets, white or red cells) that could lead to infection, bleeding, or anemia.
- **Heart:** Irregular heart rhythm or heart attack.
- **Skin:** The most likely adverse events are rash and pruritus, which generally resolve when study drug is discontinued.

Human anti-human antibodies: In preliminary analyses, emergence of anti-NIVOLUMAB antibodies following treatment has not been observed to date. Neutralizing antibodies have not been observed with the use of ipilimumab. Such antibodies were detected at baseline (pre-treatment) in 4 of 36 subjects treated with NIVOLUMAB (Protocol MDX1106-01). The reactivity in 1 of these subjects was likely due to endogenous interference in the assay, as this subject had subsequent positive post-dose results. The other 3 subjects had negative post-dose results. In the 1 subject with positive baseline and post-baseline results, there appears to have been no impact of immunoreactivity on the safety of NIVOLUMAB.

2.5. Study Duration

The expected maximum duration of NIVOLUMAB treatment for a subject is 1.25 years (60 weeks). Expected maximum duration of nivolumab with ipilimumab treatment is 12 weeks.

The expected maximum duration of a subject's participation in this study is 3 years with survival follow-up to continue indefinitely until withdrawal of consent for follow-up or death.

